1.2 Summary of Preclinical Pharmacology

1.2.1 Primary Pharmacodynamics

In monkeys administered CIVI 007 at 0.5 and 1.5 mg/kg once weekly for 4 weeks via the subcutaneous (SC) route, the PCSK9 protein in serum was reduced by compared to the baseline level, respectively. The maximum effect was achieved on Day 29, and PCSK9 levels did not fully return to pre-study values during the 8-week recovery phase. The effects were substantially greater than those seen with (the oligonucleotide moiety of CIVI 007, without GalNAc conjugate), underpinning the ability of the GalNAc moiety to drive effective liver delivery.

In the same study, CIVI 007 caused dose responsive LDL-C reductions of 53% and 70% compared to baseline, respectively, with maximum effect on Day 29; the half-life for reversal of the LDL-C reductions was days, respectively. As expected, LDL reductions were tracked by apolipoprotein (apo) B reductions. On Day 29, apoB levels were down dose dependently by respectively, and apoB levels did not return fully to baseline during the 7 weeks of recovery in either of the 2 dose groups. Weak or no effects on high-density lipoprotein cholesterol (HDL-C), total cholesterol, and triglycerides were observed.

The administration route seemed to have an effect on the intended pharmacology (serum PCSK9, plasma apoB, and LDL-C), with the intravenous (IV) route being significantly less effective than the SC route. Receptor saturation differences might account for an apparent greater effect with the more protracted distribution phase associated with SC administration than with the shorter distribution phase associated with IV administration.

[figure not shown]
1.2.2 Effect on Plasma Ceramide Levels in Monkeys

To investigate the potential effect of CIVI 007 on ceramides in monkeys, samples were drawn from 6 animals receiving 1.5 mg/kg/week for 4 weeks, on pretreatment Day -8, Day -1, and Day 29, one week after the final dose. Compared to both pretreatment days, treatment with CIVI 007 significantly decreased the levels of ceramides

In these lipid classes, the total levels and practically all molecular species within the class were decreased by approximately when compared to the pre-dose levels. This is quite similar to the effect of the PCSK9 loss of function mutation (R46L) in humans, suggesting that treatment with CIVI 007 may recapitulate the known CV benefit of this mutation. For some reason, the levels varied considerably between pre-dose samples, obscuring any potential effect of the treatment on this class of ceramides.

[figure not shown]
1.3 Summary of Safety Pharmacology and Toxicology

1.3.1 Safety Pharmacology

[figure not shown]
1.3.2 Toxicology

[figure not shown]
In the pivotal GLP toxicology studies (2-week and 13-week studies in both rats and monkeys), doses of CIVI 007 were administered SC at either weekly (2-week studies) or biweekly (13-week studies) intervals at 0, 5, 20, or 50 mg/kg/dose (rats) and 0, 3, 10, or 30 mg/kg/dose (monkeys).

Based on the combined observations in the 2 and 13-week studies, the no observed adverse effect level (NOAEL) was considered to be 20 mg/kg/dose in the rat, which corresponds to a C_{max} of and an AUC_{0-336} of (mean of both sexes on Day 85), and 30 mg/kg/dose in the monkey, which corresponded to CIVI 007 exposures (mean of both sexes on Day 85) of for $AUC_{0.5-24}$ and for C_{max} .
The genotoxic and mutagenic potential of CIVI 007 was evaluated in GLP in vitro bacterial mutagenicity and chromosomal aberrations studies and were found to be negative at maximum "limit" doses specified in regulatory guidelines.
CCI

[figure not shown]
In conclusion, it is considered that the available safety information supports the administration of CIVI 007 to volunteers in this study.

1.7 Clinical Summary

The first in human (FIH) study is a placebo controlled, single blind, randomized, Phase 1, single ascending dose (SAD) and multiple ascending dose (MAD) study to assess the safety, tolerability, pharmacokinetics (PK), and pharmacodynamics (PD) of CIVI 007 SC administered in otherwise healthy male and female subjects with an elevated LDL-C level. This study is currently ongoing

1.8 Rationale

The purpose of this study is to further investigate the early clinical profile of lower doses of CIVI 007 in patients with hypercholesterolemia and on a stable dose of background statin therapy. The principal objective of this study is to obtain safety and tolerability data when CIVI 007 is administered SC given twice over a 28-day dosing interval. This information, together with the PK and PD data, will help establish the doses and dosage regimen suitable for administration to larger groups of patients in Phase 2b and 3 clinical development.

1.9 Risk/Benefit

Patients in the current study are not expected to receive any significant, long-term health benefit (beyond that of an assessment of their medical status) from participating in the study.

The risks of participation are primarily those associated with adverse reactions to the study treatment as previously described. Based on initial observations in the ongoing Phase 1 trial, CIVI 007 has a favorable clinical profile at lower doses and number of injections to justify advancement of CIVI 007 to Phase 2a clinical development. The proposed Phase 2a study will provide robust information to determine advancement of the program to Phase 2b/3 testing.

There may also be some discomfort from collection of blood samples and other study procedures. More information about the known and expected benefits, risks, and reasonably anticipated adverse events associated with CIVI 007 may be found in the IB¹.

2 STUDY OBJECTIVES

2.1 Primary Objective

The primary objective of the study is to assess the safety and tolerability of CIVI 007 following multiple SC doses in patients on a background of a stable dose of statin therapy.

2.2 Secondary Objective

The secondary objective is to assess the PD effect of CIVI 007 on total PCSK9 and LDL-C levels in the study population.

2.3 Exploratory Objectives

The exploratory objectives include the following:

- To assess the effect of CIVI 007 on other lipid and lipoproteins including triglycerides (TG), HDL-C, non-HDL-C, very low density lipoprotein-cholesterol (VLDL-C), total cholesterol, apolipoproteins B, A-I and lipoprotein(a)
- To assess the effect of CIVI 007 on high-sensitivity C-reactive protein (hsCRP)
- To collect antidrug antibody (ADA) samples for potential future assessments of immunogenicity
- To further inform the population PK model of CIVI 007 with sparse PK sampling in patients on a background of statin therapy

3 STUDY DESCRIPTION

3.1 Summary of Study Design

This is a Phase 2a, randomized, double-blind (investigator/subject), sponsor open, parallel-group, multicenter study to evaluate the early clinical profile (safety, tolerability, PD, and PK) of CIVI 007 in patients on a background of statin therapy with or without ezetimibe. Patients are required to be on standard of care treatment for high blood cholesterol consistent with 2018 ACC/AHA guidelines¹⁴, that includes a stable dose of statin therapy for at least 4 weeks prior to the Screening Visit. The study will enroll approximately 48 patients who will be randomized to 1 of 3 active treatment groups or the placebo reference group (12 patients per active treatment group and 12 in the placebo treatment group).

All potentially eligible patients will partake in the Screening Visit up to 21 days prior to Day 1. The Screening Visit will be the first study visit.

The Treatment Period begins with the first administration of study drug on Day 1 where eligible patients will be randomized in a 1:1:1:1 ratio to one of the following treatment groups:

- Group 1: ccl mg CIVI 007 administered SC on Day 1 and Day 29
- Group 2: cci mg CIVI 007 administered SC on Day 1 followed by cci mg CIVI 007 administered SC on Day 29
- Group 3: mg CIVI 007 administered SC on Day 1 and Day 29
- Group 4: Placebo for CIVI 007 administered SC on Day 1 and Day 29

Patients will receive an initial dose of CIVI 007 or placebo at the study site on Day 1. For convenience, eligible patients will have the option to be admitted to the study site the day prior to Day 1. Patients will be discharged from the study site after completing the 8-hour post-dose follow-up assessments and will attend scheduled outpatient visits at Days 8, 15 and 22 to assess safety, tolerability, PK, and PD prior to their second dose. These visits and associated lab results will be used to assess eligibility to receive the second study drug administration. All doses will be administered in the fasted state in the morning, in accordance with a randomization schedule.

The second administration of study drug ends the Treatment Period and is to occur 4 weeks later on Day 29. Patients will again be discharged from the study site after completing the 8-hour post dose follow-up assessments. This will end the Treatment Period.

The Follow-up Period then begins and patients will attend scheduled follow-up visits at Days 36, 43, 57 and 85 to assess safety, tolerability, PK, and PD. The duration of the Follow-up Period will therefore be approximately 2 months from the last dose of study drug, unless extended follow-up is required based on Day 85 LDL-C assessments or other Investigator determined safety considerations.

[figure not shown]
Extended follow-up visits will be conducted on a monthly basis for up to 3 months if Day 85 LDL-C levels are <80% of their baseline level; extended follow-up will end within the 3-month period if LDL-C levels are ≥80% of baseline. Extended follow-up visits (frequency and assessments will be at the discretion of the Investigator) to monitor Investigator determined safety considerations may extend beyond 3 months, if deemed appropriate by the Investigator, and will continue until there are no safety observations requiring further follow-up. The total duration of

the study for each patient will be approximately 3 to 6.5 months, depending on the variable length of the screening, and follow up periods.

A Safety Review Committee (SRC) will perform interim unblinded reviews of safety, tolerability, and available PK and PD data collected for the purposes of protecting subject safety as well as providing guidance to the Sponsor on the evolving clinical profile of CIVI 007. The SRC will comprise, at a minimum, the Sponsor's clinical development contact, the study Medical Monitor, a gastroenterologist not involved in study conduct and a pharmacokineticist. A separate document will detail the SRC's operating procedures.

The study design is graphically summarized in Figure 1:

Figure 1. Summary of the Study Design

Mo = month; Q4W = Every 4 weeks; Wk = week; R = randomization;

A visit window of ± 3 days will be permitted for each study visit except for the first day of study drug administration.

Appendices A and B define the detailed Schedule of Procedures and Clinical Laboratory Analyte measures, respectively, to be performed during the study.

3.2 Study Design Rationale

Based on initial data from the ongoing FIH study and within the context of a limited experience, CIVI 007 appears to provide the expected pharmacologic profile associated with PCSK9 inhibition. CIVI 007 shows PCSK9 knockdown that begins around 12.5 mg with maximal inhibition of approximately 90% at common mg. The efficacy profile includes robust, dose-dependent reductions in atherogenic lipoproteins and lipids that appear to peak within a week following administration and are stable out to 4 weeks after administration. Changes in lipoproteins and lipids after multiple doses are consistent with those after single doses.

CIVI 007 therefore appears to have a favorable clinical profile and justify advancement to Phase 2 testing in this study. The Phase 2a study will provide robust information to determine advancement of the program to Phase 2b/3 testing. A forced up-titration dosing group (cc) mg) will provide an initial understanding of this dosing strategy on CIVI 007's clinical profile.

A parallel group design, as opposed to an ascending dose design, has been chosen as initial Phase 1 observations have demonstrated safety in the study dose range. Subcutaneous dosing has been chosen as this is the intended clinical route of administration.

Dosing and follow-up will occur in a double-blind state for the Investigator and clinical staff in order to avoid bias in the collection of data.

Conducting the study in patients with LDL-C levels in the study range and on a background of a stable dose of statin therapy (with or without ezetimibe) will enable safety, tolerability, PK, and PD data to be collected in the intended clinical population in whom additional drug treatment may be warranted to optimize their LDL-C levels.

Placebo has been chosen as the control treatment to assess whether any observed effects are treatment-related or simply reflect the study conditions.

3.3 Study Start and End of Study Definitions

The start of the study is defined as the date the first patient who is subsequently enrolled to the study signs an Informed Consent Form (ICF). The end-of-the study is defined as the date of the last patient's last assessment (scheduled or unscheduled).

3.4 Study Termination

The study may be discontinued at the discretion of the Investigator (or designee), Sponsor, or Sponsor's Medical Monitor if any of the following criteria are met:

- Medical or ethical reasons affecting the continued performance of the study
- Difficulties in the recruitment of patients and execution of the study
- Cancellation of drug development

3.5 Study Indication

Treatment of hypercholesterolemia.

4 SELECTION AND WITHDRAWAL OF PATIENTS

4.1 Inclusion Criteria

Patients who meet all of the following criteria will be eligible to participate in the study:

- 1. Willing and able to provide written and signed informed consent prior to any study-specific procedures.
- 2. Males or females, 18-70 years of age at the time of consent.
- 3. Body mass index (BMI) between 18.0 and 40.0 kg/m², inclusive, and a body weight of ≥60 kg at screening.
- 4. Currently on a stable (>4 weeks prior to the Screening Visit) dose of statin therapy (with or without ezetimibe).
- 5. Fasting LDL-C:
 - a. ≥100 mg/dL for those without any evidence of established ASCVD at the Screening Visit

or,

- b. ≥70 mg/dL for those with evidence of established ASCVD at the Screening Visit.
 - Established ASCVD is defined as a history of at least 1 of the following occurring no more recently than 3 months prior to screening:
 - o Acute coronary syndrome
 - Myocardial infarction
 - o Stroke or transient ischemic attack presumed to be of atherosclerotic origin
 - Coronary revascularization (Coronary Artery Bypass Grafting or Percutaneous Coronary Intervention)
 - o Peripheral vascular disease or revascularization
 - o In the absence of an above event, ASCVD as diagnosed >3 months prior to the Screening Visit based on invasive or noninvasive imaging such as angiography, coronary artery calcium (CAC) score >75th percentile, or >50% stenosis in any arterial bed.

Note: Retesting will be allowed once at Screening Visit for LDL-C that is in the range of 65-69 mg/dL.

6. Fasting TGs <400 mg/dL at the Screening Visit.

Note: Retesting will be allowed once at Screening Visit for TGs in the range of 401-450 mg/dL.

7. Women of childbearing potential (i.e., not postmenopausal [documented amenorrhea for ≥1 year in the absence of other biological or physiological causes] or surgically sterile including tubal ligation) must have a negative serum pregnancy test at the Screening Visit and a negative urine dipstick prior to dosing on Day 1. Postmenopausal status will be confirmed with a Screening Visit serum follicle-stimulating hormone (FSH) level >40 mIU/mL. Women aged >60 years whose FSH values are not >40 mIU/mL may be included at the discretion of the Investigator and in consultation with the Sponsor.

Participating women of childbearing potential must agree to use 2 acceptable methods of contraception throughout the duration of the study and for 30 days after the last dose of study drug. Acceptable methods of contraception include condom, nonhormonal intrauterine device, or a vasectomized partner.

8. Male participants must be willing to use condoms during sexual intercourse from the Screening Visit until at least 90 days after administration of the last dose of study drug.

4.2 Exclusion Criteria

Patients who meet any of the following criteria will be excluded from participation in the study:

- 1. Women who are pregnant, nursing or breast feeding.
- 2. Currently prescribed a lipid lowering agent other than a statin or ezetimibe.
- 3. Abnormal liver function test at the Screening Visit (aspartate aminotransferase or alanine aminotransferase >1.5 × the ULN, total bilirubin >1.5 × ULN, or alkaline phosphatase >1.5 × ULN, based on appropriate age and gender normal values). Participants with bilirubin >1.5 × ULN and a history of Gilbert's syndrome may be included.
- 4. Active liver disease as defined by the investigator (e.g., cirrhosis, alcoholic liver disease, hepatitis B virus, hepatitis C virus, autoimmune hepatitis, liver failure, and/or liver cancer) or history of liver transplant. NASH is considered exclusionary while non-alcoholic fatty liver (NAFL) is not exclusionary.
- 5. Known diagnosis of human immunodeficiency virus.
- 6. Mild, moderate or severe renal insufficiency, defined as an estimated glomerular filtration rate (eGFR) <60 mL/min/1.73m² (calculated using the Chronic Kidney Disease Epidemiology Collaboration eGFR formula), at the Screening Visit.
- 7. Uncontrolled thyroid disease: hypothyroidism or hyperthyroidism, as defined by thyroid-stimulating hormone below the lower limit of normal or >1.5 × ULN, respectively, based on results from the Screening Visit. If controlled, treatment should be stable for at least 3 months prior to the Screening Visit.
- 8. Type 1 diabetes mellitus or uncontrolled type 2 diabetes mellitus, defined as hemoglobin A1c (HbA1c) value >9%, based on results from the Screening Visit.
- 9. New York Heart Association Class II, III, or IV heart failure.
- 10. Myocardial infarction, severe or unstable angina pectoris, coronary revascularization, or other major cardiovascular event(s) resulting in hospitalization within 3 months of the Screening Visit.
- 11. Uncontrolled cardiac arrhythmia or prolonged QT interval on the Screening Visit or the pre-dose Day 1 ECG (QT corrected using Fridericia's formula [QTcF] >450 msec for men and >470 msec for women), or known family history of prolonged QT interval or unexplained sudden cardiac death.
- 12. Currently receiving cancer treatments or, in the Investigator's opinion, is at risk of relapse for recent cancer within the study period.
- 13. A history of autoimmune disorder(s).

- 14. A history of hematologic or coagulation disorders.
- 15. Abnormal PT, aPTT, or INR at the screening visit.
- 16. Concomitant antiplatelet or anticoagulation medication. Allowable are low-dose aspirin (81 mg or less, daily) for CVD risk reduction, or PRN for occasional pain relief. Other antiplatelet drugs (e.g., P2Y12 inhibitors) and all anticoagulants are exclusionary.
- 17. Except as noted above, patients who have a clinically significant disorder that, in the opinion of the Investigator, could contraindicate the administration of study drug, affect compliance, interfere with study evaluations, or confound the interpretation of study results
- 18. History of drug or alcohol abuse within the past year.
- 19. Previous treatment with CIVI 007.
- 20. Participation in another clinical study of an investigational agent or device concurrently or within 1 month prior to the Screening Visit or use of an investigational agent within 1 month or 5 half-lives (if known), whichever is longer, prior to the Screening Visit.
- 21. Donation of blood from 3 months prior, plasma 2 weeks prior, and platelets 6 weeks prior to the Screening Visit.
- 22. Any other findings that, in the opinion of the Investigator, would compromise the participant's safety or participation in the study.

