The inhibition of PCSK9 is one novel approach being taken to overcome the residual shortcomings of statin therapy. As PCSK9 acts to inactivate LDL-R, its inhibition reverses this process and has been shown to cause a decrease in plasma LDL levels of up to 60% in humans. Currently, 2 monoclonal antibodies (mAbs) to PCSK9 have been approved for clinical use, and 2 outcomes trials have shown reductions in CV events, thus validating the clinical benefit of inhibiting the PCSK9 target. The PCSK9 mAbs (evolocumab, alirocumab) target only the circulating levels of PCSK9 and have the potential for production of antidrug antibodies. Common side effects include injection site reactions, common cold, and influenza. Serious allergic reactions have also been reported.

An alternative approach to reducing the impact of PCSK9 on LDL-C is blocking its production at the level of messenger ribonucleic acid (mRNA) using an antisense inhibitor complementary and specific to human PCSK9 mRNA. Compared to mAb therapy, this mode of action will have the advantage of blocking both intra- and extracellular PCSK9 levels, reducing the potential for antidrug antibody formation and impacting novel ASCVD risk biomarkers such as ceramides. ¹⁰ In addition, due to its high potency and long half-life in liver administration of CIVI 007 to human subjects, CIVI 007 treatment is expected to lead to stable reductions in LDL-C when dosed

monthly at a single low volume dose (**cc)** mg), thus improving patient convenience and compliance and potentially reducing local pain at the injection site compared to mAbs that can require 3 injections of each 1.5ml or an on-body infusor when dosed monthly.

CIVI 007 is currently under development by CiVi Biopharma, Inc. (CiVi, hereinafter). CIVI 007 is an antisense inhibitor complementary to human PCSK9 mRNA and is based on the Locked Nucleic Acid (LNA) drug platform, which was pioneered by Santaris Pharma. The LNA oligonucleotide is designed to specifically bind to, and degrade, the mRNA encoding PCSK9, using the endogenously expressed enzyme, ribonuclease H, to cleave the mRNA. To facilitate optimal delivery of the drug to the intended target organ (liver), the LNA oligonucleotide is conjugated to a galactose/N-acetylgalactosamine (GalNAc) moiety that facilitates functional uptake by hepatocytes through binding to the surface expressed asialoglycoprotein receptor.

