5.6 Prior and Concomitant Medications and/or Procedures

5.6.1 Excluded Medications and/or Procedures

Once eligibility is determined, and until study completion, patients are to be counseled from use of any new, or change in dose, of any prescription or nonprescription medications/products. Specific attention is to be paid to maintaining the concurrent dose of statin/ezetimibe therapy during the course of the study.

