5.6.2 Restricted Medications and/or Procedures

Patients are restricted from using any new prescription or over-the-counter cholesterol lowering medication. In addition, until completion of follow-up, change in the concurrent dose or discontinuation of statin/ezetimibe medication during the course of the study is prohibited unless deemed medically necessary by the Investigator (or designee) or the patient's medical care provider.

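### Exclusion 2 has no look-back, so a patient who has just stopped a marketed PCSK9 antibody or other lipid drug can enter with a baseline that is still drifting

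*Protocol*

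**What the plan says.** Exclusion 2 reads the same in the synopsis and in Protocol 4.2. It excludes a patient who is "Currently prescribed a lipid lowering agent other than a statin or ezetimibe", which tests status at one moment.

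Exclusion 20 does look back, barring "use of an investigational agent within 1 month or 5 half-lives (if known), whichever is longer, prior to the Screening Visit", but only for investigational products. Inclusion 4 (Protocol 4.1) requires a patient to be "Currently on a stable (>4 weeks prior to the Screening Visit) dose of statin therapy (with or without ezetimibe"), so its four-week clause is attached to the statin dose.

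On-study rules start later. Protocol 5.6.1 applies "Once eligibility is determined, and until study completion, patients are to be counseled from use of any new, or change in dose" of prescription or non-prescription products. Protocol 5.6.2 adds: "Patients are restricted from using any new prescription or over-the-counter cholesterol lowering medication". Both concern new or changed use from entry onwards, not what was stopped before entry.

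Protocol 1.1 supplies the context: "Currently, 2 monoclonal antibodies (mAbs) to PCSK9 have been approved for clinical use", and PCSK9 inhibition "has been shown to cause a decrease in plasma LDL levels of up to 60% in humans".

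Baseline is the Day 1 pre-dose value (SAP 3.1.3). The secondary endpoints are percent change from it in LDL-C and PCSK9 at Days 29, 57 and 85, analysed by ANCOVA with treatment and baseline (SAP 3.4.1). There are about 12 patients per arm.

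**The concern.** A patient whose marketed PCSK9 antibody, fibrate or niacin was stopped shortly before Screening is no longer currently prescribed it and passes exclusion 2. The same kind of agent taken as a study drug would have to be washed out under exclusion 20.

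If the earlier drug is still wearing off on Day 1, LDL-C will rise afterwards for a reason unrelated to CIVI 007. The Day 1 value is both the denominator of the percent change and the ANCOVA covariate. The covariate cannot repair this. The model sees a low baseline and cannot distinguish a patient whose level is stably low from one whose level is temporarily suppressed and rising.

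No later rule catches such a patient. The Per-Protocol Population removes only major protocol deviations (SAP 3.2.2), and here no criterion was breached.

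**Working it through.** **Step 1: does another clause close the gap?**

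- Exclusion 17 mentions confounding of study results, but its subject is "patients who have a clinically significant disorder that, in the opinion of the Investigator, could contraindicate the administration of study drug" or have similar effects. It concerns a disorder, not earlier medication.
- Exclusion 22 is general investigator discretion and states no rule about lipid drugs.
- Exclusion 20 covers investigational agents only.
- Sections 5.6.1 and 5.6.2 govern new use and changes after eligibility is settled.

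None sets a washout for a marketed lipid drug.

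**Step 2: how large could the effect be?** The documents state no figure on this point, so there is nothing to reproduce. The inputs are:

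- n = 12 per arm (Protocol 9.2.4).
- s, the fraction of LDL-C still suppressed at Day 1. This is not in the documents and is shown at 10%, 20% and 30%.
- Full wear-off by the endpoint visit (assumption).
- True effect of study drug: none on placebo; a 50% fall on active drug (illustrative assumption).

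Let L be the unsuppressed LDL-C, so the measured baseline is L(1 − s).

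Placebo: the endpoint value is L, so the spurious change is 1/(1 − s) − 1 = s/(1 − s). One patient shifts the arm mean by that amount divided by 12.

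Active: the endpoint value is 0.5L, so the reading is 0.5/(1 − s) − 1 instead of −0.5. The error is 0.5 × s/(1 − s), again divided by 12 for the arm mean.

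| s | Placebo patient's spurious change | Placebo-arm shift | Active patient reads (true −50%) | Active-arm shift |
|---|---|---|---|---|
| 10% | +11.1% | 11.1/12 = +0.9 points | −44.4% | 5.6/12 = +0.5 points |
| 20% | +25.0% | 25.0/12 = +2.1 points | −37.5% | 12.5/12 = +1.0 points |
| 30% | +42.9% | 42.9/12 = +3.6 points | −28.6% | 21.4/12 = +1.8 points |

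**Step 3: does the LDL-C entry floor block these patients?** With suppression s at Screening, the unsuppressed level needed to pass is 70/(1 − s) mg/dL with established ASCVD, or 100/(1 − s) mg/dL without. At 10% that is 77.8 or 111.1; at 20%, 87.5 or 125.0; at 30%, 100.0 or 142.9. The floor screens out some suppressed patients but not all.

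**Step 4: does the gap between Screening and Day 1 help?** Protocol 3.1 allows up to 21 days and sets no minimum. Some wear-off may happen before baseline, but none is guaranteed.

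**Step 5: ezetimibe.** The synopsis (study design) and SAP 2.2.1 put the with-or-without-ezetimibe phrase inside the sentence requiring at least four weeks of stability. Protocol 3.1 gives the same sentence without it, and inclusion 4 ties the four weeks to the statin dose. The passages do not agree on whether ezetimibe is covered.

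**The case against.** Several points on the other side stand.

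- **Randomisation.** Rare carry-over is not expected to favour any arm, and the placebo group exists to separate drug effects from study conditions (Protocol 3.2). A reader might infer that the treatment comparison is biased. The documents do not support that; only noise and chance imbalance follow.
- **Size.** Every figure depends on an assumed s and assumed timing. The 60% in Protocol 1.1 is the maximum effect of PCSK9 inhibition, not what remains after stopping. The documents say neither how long a stopped drug acts nor how many candidates have used one. A reader might apply the placebo shifts to every arm, but three of the four arms are active, and there the shift is smaller.
- **Over-the-counter products.** A reader might infer that any user has a distorted baseline. Constant use lowers baseline without distorting percent change, and 5.6.1 counsels against dose changes. Only a recent start, stop or change matters.
- **Ezetimibe.** A reader might infer that ezetimibe begun days before Screening plainly passes. Given the synopsis and SAP wording, this is an ambiguity, not a clear permission.
- **Detection.** SAP 3.3.6 lists prior medications for all randomised subjects, so a case may be visible. SAP 3.4.1 would explore a Wilcoxon test if residuals are not normal, which dampens an outlier. Neither step restores a valid baseline or removes the patient from the analysis.
- **Priority.** The primary objective is safety, and the sample size was not based on power. This lowers the stakes but leaves the gap open.

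**Conclusion.** The gap is real and no other clause closes it. A patient recently off a marketed lipid drug can be enrolled without a deviation and bring a drifting baseline into both secondary endpoints.

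The consequence is modest: extra variability and possible chance imbalance at 12 per arm. Under the stated assumptions (one affected patient, 10% to 30% residual suppression, full wear-off), the LDL-C arm mean moves by about 1 to 4 points on placebo. It moves by about 0.5 to 2 points in an active arm with a true 50% fall. Partial wear-off would give less, and more affected patients or greater suppression would give more. No size is offered for PCSK9, because the documents give no figure for the effect of an earlier antibody on it. The frequency of such patients is also unknown.

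**What to change.** 1. In exclusion 2, in both the synopsis and Protocol 4.2, replace the current-prescription test with use within a stated period before Screening. It should apply to any lipid-lowering agent other than a statin or ezetimibe and should name marketed PCSK9-directed agents. The formula in exclusion 20 (1 month or 5 half-lives, whichever is longer) is available as a model; the sponsor should confirm whether that length suits these drugs.
2. For non-prescription cholesterol-lowering products, require only stable use over the same window, so that harmless constant users are not excluded.
3. Reconcile inclusion 4 and Protocol 3.1 with the synopsis and SAP 2.2.1, so that the four-week stability rule clearly covers ezetimibe when it is used.

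The cost is a short protocol amendment, a few screen failures or delayed entries, and a prior-medication question at Screening that covers the window. That question is needed because Protocol 6.1 and 5.6.4 provide for recording concomitant and on-study medication and state no look-back of this length.
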